1.2.3 Autonomy

The BP design's primary consideration is autonomy. Apart from body weight for initialization, the BP requires no quantitative input from, or participation by, the user. The BP also remains autonomous in dose handling when the CGM is offline, whereby it (i) invokes a high-resolution "basal-rate profile" that it had recently learned when the CGM was online, (ii) responds to meal announcements based on what is

had learned about them when the CGM was online, and (iii) automatically responds to user-entered BG values by issuing a correction dose of insulin or glucagon. Thus, the BP never relies on the user with dose determination decisions and provides a turnkey glucose-control solution across a broad range of individual needs.

1.2.4 Insulin-only Versus Bihormonal Configurations

In the insulin-only configuration, all features of the BP operate as usual except that glucagon is not given. In addition, the lowest glucose target that can be chosen by the user is increased from 100 mg/dl in the bihormonal configuration to 110 mg/dl in the insulin-only configuration. This works to reduce the aggressiveness of insulin dosing in the insulin-only configuration relative to the bihormonal configuration, with the aim of keeping the amount of hypoglycemia low even at the potential cost of relatively raising the mean glucose level. On the other hand, the synergy of having both insulin and glucagon administration capabilities activated in the bihormonal configuration is expected to provide better glucose control with reduced hypoglycemia.

The primary intended use for the insulin-only configuration of the BP system is to provide automated glucose control prior to commercial availability of a stable glucagon analog. Moreover, when in the bihormonal configuration, the BP will automatically invoke the insulin-only configuration during periods whenever glucagon delivery is not possible.

1.3 BP System Embodiments

The BP hardware platform began as a laptop-driven system, which we used in all of our inpatient studies (2008–2012) at MGH. The BP embodiment was then transformed to a mobile wearable iPhone-Based system, which was used in our initial outpatient and home-use studies (2013–2017). From 2018 onwards, Beta Bionics transformed the system design into the iLet® Bionic Pancreas System (iLet), a fully integrated wearable device intended to undergo final clinical studies in order to be commercialized. Below are descriptions of and the outpatient clinical results that were obtained using the iPhone-based BP and the iLet.

1.3.1 iPhone-Based BP System

The iPhone-Based BP system consisted of the t:slim infusion pump (Tandem), a G4 or G5 CGM (Dexcom), and the BP control algorithms running on an iPhone app that has a graphical user interface (GUI). The iPhone and the Dexcom CGM receiver were hardwire connected and housed together in a custom enclosure, with the iPhone controlling the t:slim pump through Bluetooth. The BP app provided a user interface to make meal announcements by selecting the meal type (as “breakfast,” “lunch,” or “dinner”) and meal size (qualitatively as “larger than typical,” “typical,” “smaller than typical,” or “just a bite”). The BP app also reported associated system alarms and communicated to a server that allows remote telemetric study monitoring.

Using our iPhone-based BP, we have conducted over 110 outpatient experiments of 5–11 days in duration in each participant with T1D (> 800 patient days or > 2 patient years of data), and across participants ranging in age between 6 and 76 years old and in body mass between 21 and 133 kg. The robust adaptation capabilities of our BP are evident from the fact that the average total daily dose of insulin among these participants varied by over 13-fold (from 11 to 145 units/day) among children and adults with T1D. Additionally, the iPhone-based BP was used in the bihormonal configuration in subjects with

congenital hyperinsulinism after subtotal pancreatectomy, in the glucagon-only configuration as an adjunct to patient-controlled insulin dosing in adults with T1D or as an adjunct to usual therapy in adults with post-bariatric hypoglycemia, in the insulin-only configurations in adults with insulin-dependent type 2 diabetes, and in both configurations in adults with cystic fibrosis-related diabetes.

Table 1. iPhone BP System Studies

Year	Name of Study	Setting, Date span	Cohort studied	Duration & device exposure*	Configuration & Set Points	Medication s used	Protocol Description, Outcome, if applicable.	Result: Mean CGM, % CGM < 60 mg/dl
2013	Beacon Hill IDE: G120255 11-2012	Supervised hotel stay Start-End: 02-2013–09-2013	20 adults aged ≥21	5 days 2,400 hours	Bihormonal 100 mg/dl iPhone and two Tandem t:slim pumps	Insulin lispro (Eli Lilly) Glucagon (Eli Lilly)	RCT with usual care at home Direct supervision	BP: 133±13 mg/dl, 1.5% UC: 158±30 mg/dl, 3.7%
	2013 Summer Camp IDE: G130065 04-2013	Supervised summer setting Start-End: 07-2013–08-2013	32 adolescent s aged 12–18	5 days 3,840 hours	Bihormonal 100 mg/dl iPhone and two Tandem t:slim pumps	Insulin lispro (Eli Lilly) Glucagon (Eli Lilly)	RCT with usual care at camp Remote telemetric monitoring	BP: 142±12 mg/dl, 1.3% UC: 158±27 mg/dl, 2.2%
2014	2014 Summer Camp IDE: G130065 04-2013	Supervised camp setting Start-End: 07-2014–08-2014	19 pre-adolescent s aged 6–11	5 days 2,280 hours	Bihormonal 100 mg/dl iPhone + two Tandem t:slim pumps	Insulin lispro (Eli Lilly) Glucagon (Eli Lilly)	RCT with usual care at camp Remote telemetric monitoring	BP: 137±11 mg/dl, 1.2% UC: 168±30 mg/dl, 2.8%
	BP Multi-center IDE: G140045 04-2014	Outpatient , home, 4 study sites Start-End: 05-2014–03-2015	39 adults aged ≥18	11 days 10,296 hours	Bihormonal 100 mg/dl iPhone and two Tandem t:slim pumps	Insulin lispro (Eli Lilly) Insulin aspart (Novo Nordisk) Glucagon (Eli Lilly)	RCT with usual care Remote telemetric monitoring	BP: 141±10 mg/dl, 0.6% UC: 162±29 mg/dl, 1.9%
2015 - 2016	BP Set Point IDE: G150130 JUL-2015	Outpatient , unsupervised at home Start-End: 08-2015–12-2016	20 adults aged ≥18	8 arms, 4 days each 15,360 hours	Bihormonal and Insulin-only Bihormonal: 100, 110, 115, 130 mg/dl Insulin-only: 110, 120, 130, 145 mg/dl iPhone and one or two Tandem t:slim pumps	Insulin lispro (Eli Lilly) Insulin aspart (Novo Nordisk) Glucagon (Eli Lilly)	RCT with usual care and 8 different BP configurations testing different glucose target set points in addition to insulin only for the first time Both configurations at 110 mg/dl and 130 mg/dl included an exercise challenge to induce hypoglycemia under direct observation in the clinic Results helped identify the glucose target settings that will be used in future studies. These were set to range from 110 mg/dl to 130 mg/dl, with a default of 120 mg/dl in the insulin-only configuration, and set to range from 100 mg/dl to 120 mg/dl, with a default of 110 mg/dl in the bihormonal	Bihormonal: 100 mg/dl: 136±14 mg/dl, 0.8% 110 mg/dl: 148±17 mg/dl, 0.4% 115 mg/dl: 146±15 mg/dl, 0.9% 130 mg/dl: 156±12 mg/dl, 0.5% Insulin-only 110 mg/dl: 153±15 mg/dl, 1.3% 120 mg/dl: 156±15 mg/dl, 1.1% 130 mg/dl:

							configuration	161 ± 17 mg/dl, 0.8%
							Remote telemetric monitoring	145 mg/dl: 174 ± 23 mg/dl, 1.0% UC: 158 ± 31 mg/dl, 1.4%
2015 - 2016	Stanford Insulin-only IDE: G150142 JUL-2015	Outpatient, unsupervised at home	16 adults aged ≥ 18	2 arms, 7 days each	Insulin-only 115 to 130 mg/dl	Insulin lispro (Eli Lilly)	RCT with usual care Results helped identify the glucose target settings that will be used in future studies	BP: 160 ± 9 mg/dl, 0.9% UC: 151 ± 26 mg/dl, 1.9%
				5,376 hours	iPhone and one Tandem t:slim pump	Insulin aspart (Novo Nordisk)	Remote telemetric monitoring	
2017	Monitoring IDE: G150130 JUL-2015	Outpatient, unsupervised at home	23 adults aged ≥ 18	4 arms, 7 days each	Bihormonal and Insulin-only Bihormonal: 100 mg/dl Insulin-only: 110 mg/dl	Insulin lispro (Eli Lilly) Insulin aspart (Novo Nordisk) Glucagon (Eli Lilly)	RCT with one usual care arm and two BP arms, each repeated with and without remote monitoring Each arm repeated with and without remote telemetric monitoring Results confirmed that the insulin-only and bihormonal BP set at their lowest targets (110 and 100 mg/dl, respectively) are safe to be used in outpatient setting without remote monitoring for hypoglycemia	With monitoring: Insulin-only: 151 ± 13 mg/dl, 1.6% Bihormonal: 139 ± 13 mg/dl, 1.0% UC: 164 ± 29 mg/dl, 1.3% Without monitoring: Insulin-only: 148 ± 11 mg/dl, 1.7% Bihormonal: 139 ± 11 mg/dl, 1.0% UC: 165 ± 29 mg/dl, 2.0%
2016 - 2017	Zealand Feasibility Study IDE: G160012 FEB-2016	Supervised, in clinic	10 adults aged ≥ 18	2 arms, 8 hours each	Bihormonal 100 mg/dl iPhone and two Tandem t:slim pumps	Insulin lispro (Lilly) Insulin aspart (Novo Nordisk) Glucagon, 1 mg/ml (Lilly) Dasiglucagon, 1 mg/ml (Zealand)	RCT comparing Eli Lilly glucagon with dasiglucagon in clinic setting BP was challenged with participants wearing their own insulin pump in addition to the BP insulin dosing, with up to two times their normal basal running and a full meal bolus via their own pump. There was an exercise challenge in the late post-prandial period Direct supervision	Dasiglucagon: 110 ± 29 mg/dl, 13% Lilly glucagon: 99 ± 22 mg/dl, 20%

*Total device exposure is calculated based on cohort size used in the final study analysis

1.3.2 Fully Integrated iLet® BP System (Beta Bionics)

The iLet® Bionic Pancreas System (iLet) is a wearable device that integrates CGM technology via its built-in Bluetooth radio, two independent motor–drivetrain pumping mechanisms, which independently deliver insulin and glucagon from glass cartridges, and embedded software that includes our adaptive control algorithms. The iLet is compatible with three insulin analog formulations (insulin lispro, Lilly; insulin aspart and Fiasp, Novo Nordisk) and one glucagon analog (dasiglucagon, Zealand Pharma). The

iLet also includes a touchscreen display that provides a custom graphical user interface. In addition to the iLet ready-to-fill glass insulin cartridge and the prefilled glass dasiglucagon cartridge, the iLet uses separate insulin and glucagon administration sets, each with a proprietary connector to connect to its respective. Figure 1 illustrates the iLet's system components and a summary of its virtues and capabilities.

The iLet® Bionic Pancreas

Figure 1 Illustration of the iLet (Beta Bionics, Inc.) system components and capabilities. It is interoperable with one of two CGM devices and is compatible with three insulin analog formulations and one glucagon analog.

Additionally, the iLet continually provides daily insulin dosing recommendations (for temporary self-management, should the iLet become temporarily unavailable, e.g. broken or lost), specifically (i) four 6-h basal rates for pump therapy or a 24-h long-acting basal dose for MDI therapy, (ii) a “correction factor” for insulin doses, and (iii) prandial insulin doses for the three main meals of the day. These are direction outcome of the autonomous learning capability of the iLet’s three insulin controllers (basal, correction, and meal-dose controllers).

1.3.3 Table 2. iLet BP System Studies

Year	Name of Study	Setting, Date span	Cohort studied	Duration & device exposure ¹	Configuration & Set Points	Medications used	Protocol Description, Outcome, if applicable.	Result: Mean CGM, % CGM < 60 mg/dl
2018	Adult Bridging study IDE: G180083 MAY-2018–OCT-2018	Outpatient, unsupervised at home, centers Start-End: MAY-2018–OCT-2018	34 adults aged ≥18 completed all three arms (36 started)	3 arms, 7 days each 11,424 hours	Insulin-only 120 mg/dl Gen 3 iLet MGH used Senseonics Eversense CGM, Stanford used	Insulin lispro (Eli Lilly) Insulin aspart (Novo Nordisk) Fiasp PumpCart (Novo Nordisk)	RCT with one usual care arm and 2 BP arms, where one BP arm used insulin lispro/aspart, the other BP arm used Fiasp. The BP was set at the default glucose target of 120 and tmax setting of 65 minutes for both arms Remote telemetric monitoring Remote telemetric monitoring. Results demonstrated that the insulin-only iLet BP was safe and	BP: 155±13 mg/dl, 1.2% BP with Fiasp: 154±11 mg/dl, 1.3% UC: 163±26 mg/dl, 1.3%

					Dexcom G5 CGM		effective using both Fiasp or lispro/aspart at the default PK settings, consistent with results of the iPhone BP studies, paving the path for a larger & longer study with same device settings and insulins	
2018	Day-camp Transitional Study IDE: G180083 MAY-2018	Supervised day camp, followed by unsupervised home nightly, 2 centers Start-End: JUL-2018–AUG-2018	20 children aged 6-17	5 days 2,400 hours	Insulin-only 120 mg/dl Gen 3 iLet	Insulin lispro (Eli Lilly) Insulin aspart (Novo Nordisk)	RCT comparing usual care with BP Remote telemetric monitoring Results demonstrated that under stressful conditions, the insulin-only iLet BP was safe and effective to use in adolescents and pre-adolescents, preparing the path for a larger and longer study using the same device settings in this age group	BP: 163±15 mg/dl, 0.9% UC: 160±27 mg/dl, 0.9%
2019	Fiasp Exploratory Study IDE: G180150 JUL-2018	48 hour supervised hotel stay, followed by unsupervised home, 5 days Start-End: MAR-2018–MAY-2018	24 adults aged ≥18, 8, Tmax=65, 8, Tmax=50, 8, Tmax=40	3 cohorts, 8 subjects ≥18 each. 2 arms, 7 days each 8,064 hours	Insulin-only 120 mg/dl Gen 3 iLet	Fiasp PumpCart (Novo Nordisk)	RCT to compare default insulin PK settings (tmax = 65 minutes) with faster PK settings (tmax = 50, 40 and 30 minutes). Faster PK setting was escalated over three cohorts of 8 subjects Remote telemetric monitoring	Cohort #1, Tmax=65 157.7 mg/dl, 0.89% Cohort #1, Tmax=50 150.3 mg/dl, 0.98% Cohort #2, Tmax=65 157.6 mg/dl, 0.50% Cohort #2, Tmax=40 150.1 mg/dl, 0.69% Cohort #3, Tmax=65 152.5 mg/dl, 0.37% Cohort #3, Tmax=30 144.1 mg/dl, 0.61%
2019	Bihormonal Crossover Study IDE: G190028 FEB-2019	Outpatient, unsupervised at home Start-End: MAY-2019–JUN-2019	10 adults aged ≥18	2 arms, 7 days each 3,360 hours	Bihormonal and Insulin-only Bihormonal: 110 mg/dl Insulin-only: 110 mg/dl Gen 3 iLet	Insulin lispro (Eli Lilly) Insulin aspart (Novo Nordisk) Dasiglucagon, 4 mg/ml (Zealand Pharma)	RCT to compare insulin-only with bihormonal using dasiglucagon, testing bihormonal iLet for the first time Remote telemetric monitoring	Bihormonal: 139±11 mg/dl, 0.69% Insulin-only: 149±13 mg/dl, 1.38%

*Total device exposure is calculated based on cohort size used in the final study analysis

2 Objectives

2.1 Primary objective

To assess the feasibility of deploying the iLet bionic pancreas system in the insulin-only configuration to

pump-naïve MDI users with type 1 diabetes, in the setting of being recruited from community-based primary care practices and being trained and managed by primary care providers (PC group), and in pump- and CGM-experienced (sensor-augmented pump or hybrid closed-loop) users with type 1 diabetes recruited from, trained, and managed by an academic endocrinology practice (EN group). In both practice settings, the exclusive use of telehealth (TH) visits will be assessed, as will use of in-person (IP) visits.

We will enroll 40 adult volunteers (18-85 years old) with type 1 diabetes, 20 who are insulin pump naïve MDI users enrolled from community primary care practices by University of Colorado Family Medicine (PC group) and 20 who are technology-savvy sensor-augmented pump or hybrid closed-loop users enrolled by the Massachusetts General Hospital Diabetes Clinical Research Center (EN group). Ten of the participants at each center will be trained and managed throughout the trial using in-person visits (PC-IP and EN-IP groups) and the other ten from each center will be trained and managed throughout the trial exclusively via telehealth visits (PC-TH and EN-TH groups). The 40 participants will be evenly divided into these four groups, but not by randomization. Participants will be assigned to either the in-person or telehealth arm based on the participant's preference, the participant's location, and the discretion of the investigator. Subjects in all four groups will each participate, in random order, in one 14-day study arm under their own usual care (UC arm) and one 14-day study arm under the insulin-only configuration of the iLet bionic pancreas (iLet arm).

Our hypothesis is that pump naïve community-based primary care participants can be successfully started on the iLet bionic pancreas system by primary care providers in-person and via telehealth and that we will see similar glucose control by the iLet in the primary care and academic endocrinology groups and in the telehealth and in-person groups, with a target mean glucose of < 183 mg/dl in all four groups (PC-IP, PC-TH, EN-IP, and EN-TH). This target of < 183 mg/dl is a functional and clinically meaningful threshold for each group, consistent with a quality indicator of diabetes management (estimated HbA1c < 8.0%) that corresponds to the NCQA HEDIS measure of "HbA1c control" and which is therefore used frequently by many payers, reporting, and accrediting bodies. The outcome is categorical, and the primary outcome is not a direct comparison of the mean CGM glucose between the groups.

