2.2 Secondary objectives

1. To obtain preliminary data on the quality of glycemic control among the PC and EN groups, with separate analyses in the IP and TH sub-groups, and in the UC and iLet arms within those groups, which will be used to power a larger study with a glycemic control metric as the primary outcome. Our hypotheses are that glycemic control, with key outcomes being group mean CGM glucose, the group mean time with CGM glucose less than 54 mg/dl, and the group mean time with CGM glucose in the 70–180 mg/dl range, will be similar in the PC-IP group and the EN-IP group, and in the PC-TH group and the EN-TH group in the iLet arm. Additionally, we hypothesize that glycemic control will be similar in the PC-TH group and the PC-IP group, and in the EN-TH group and the EN-IP group in the iLet arm. Further, we hypothesize that there will be a larger difference in glycemic control metrics between the UC arms versus the iLet arm in the PC group than there will be in the EN group.
2. To assess the impact of the insulin-only configuration of the iLet bionic pancreas system on psychosocial outcomes (including quality of life, fear of hypoglycemia, and diabetes distress) among study participants. Secondary analyses will be conducted between the telehealth and in-

person arm, the EN and PC groups, and the iLet and UC arms.

3 Participant Selection

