3.1 Inclusion Criteria

1. Age 18-85 years, BMI ≥ 18.5 , have had clinical type 1 diabetes for at least one year, and have taken insulin for at least 1 year
 - a. Prescription diabetes medication regimen stable for > 1 month, including any adjunctive anti-diabetic medications (except for medications that will not affect the safety of the study and are not expected to affect any outcome of the study, in the judgment of the site principal investigator)
 - b. This does not include changes to any insulin doses, including basal rates/long-acting insulin doses, carbohydrate to insulin ratios and correction factors
2. Willing to wear one Dexcom CGM transmitter and sensor (sensor must be changed every 10 days), and one infusion set that must be replaced at least every 3 days.
3. Endocrinology practice criterion is that diabetes is managed using sensor-augmented insulin pump therapy or artificial pancreas therapy for ≥ 3 months)
4. Primary care practice criteria are that diabetes is managed by multiple daily insulin injections (insulin-pump naïve).
5. TH group criterion is that participant must have hardware and internet access capable of 2-way video and audio communication

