5.5.2 Prior to Randomization

- Psychosocial questionnaires (including quality of life, fear of hypoglycemia, diabetes distress).
- HbA1c assessment using a validated method (a value within 2 weeks prior to enrollment is acceptable)

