5.5.3 Randomization of Study Arm Sequence

Participants will be recruited specifically into the in-person or telehealth cohorts, based on their circumstances. Once the participant has been enrolled and eligibility has been established, participants within each of these cohorts will be randomized to one of two possible study arm sequences.

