6.7 Statistical Analyses

An intention-to-treat analysis will be performed. Descriptive statistics will be used to summarize patient characteristics and assessments. We will estimate the percentage of participants who have a mean sensor glucose <183 mg/dl in the iLet arms of all four groups (PC-IP, PC-TH, EN-IP, EN-TH), along with confidence intervals using the Clopper-Pearson method. The hypothesis is that there is no difference in the percentage of each group that meet this metric.

The primary analysis of the designated endpoints will be calculated on an intention-to-treat basis. In cases where an arm was not completed, we will use the available data from that arm in the data analysis. We will calculate percentages, means, standard deviations (and medians and interquartile ranges as appropriate), and ranges in descriptive analyses. Unless otherwise specified, continuous data will be summarized by presenting the number of non-missing observations, mean and standard deviation (SD) or median, minimum, and maximum. Categorical data will be summarized by presenting the number of patients and percentage for each category. We will use the t-test for comparisons of means for normally distributed outcomes and the Mann-Whitney U test for comparisons of medians on non-normally distributed outcomes between groups (PC-IP, PC-TH, EN-IP, EN-TH). We will use the paired t-test for comparison of means for normally distributed outcomes and the Wilcoxon Signed Rank test for comparisons of medians on non-normally distributed outcomes when comparing between iLet and usual care within groups. There will be no adjustments for multiple comparisons.

We may, in exploratory analyses, also stratify subjects for secondary analyses of the pre-specified endpoints by the following characteristics: sex, age, usual care insulin total daily dose, body mass index, baseline A1c, and use of CGM in usual care.

P-values can be displayed to aid interpretation, not for inference. Tables, figures and listings of all primary, secondary and safety endpoints will be created.

Data from periods when the bionic pancreas was not in use will be included, if available (Dexcom CGM data may not be available in some failure modes).

All questionnaire data (including quality of life data) for patients who have completed a minimum of 4 days with a device will be included. Results will be compared by Wilcoxon signed-rank test.

6.7.1 *Safety Analyses*

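### Telehealth v in-person and primary care v endocrinology are not randomised contrasts, yet iLet-arm control is compared between them without adjustment for baseline HbA1c

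*Combined protocol and SAP*

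**What the plan says.** Section 2.1 states: "The 40 participants will be evenly divided into these four groups, but not by randomization". Participants are "assigned to either the in-person or telehealth arm based on the participant's preference, the participant's location, and the discretion of the investigator". Section 5.5.3 repeats this for the cohorts ("Participants will be recruited specifically into the in-person or telehealth cohorts, based on their circumstances") and randomises only the sequence of the two study arms. Section 3.1 adds a condition for telehealth (TH) that in-person (IP) participants do not face: "TH group criterion is that participant must have hardware and internet access capable of 2-way video and audio communication".

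PC and EN are defined in sections 2.1 and 3.1 by site and by treatment history. PC participants are pump-naive injection users at the Colorado site. EN participants are experienced pump or hybrid closed-loop users at the Massachusetts site.

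Section 2.2 expects similar iLet-arm mean glucose, time below 54 mg/dl and time in 70–180 mg/dl for PC v EN within each visit mode. For visit mode within each practice it says, for example, "we hypothesize that glycemic control will be similar in the PC-TH group and the PC-IP group". Section 6.7 gives the method for comparing the four groups: "We will use the t-test for comparisons of means for normally distributed outcomes and the Mann-Whitney U test". It names no covariate. Baseline A1c appears there only in a list of characteristics by which the data may be stratified in exploratory work. The measurement itself is planned for everyone before randomisation (section 5.5.2: "HbA1c assessment using a validated method"; also section 6.1.1).

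**The concern.** Where people choose, or are chosen for, a visit mode, the TH and IP groups may differ in ways that also affect glucose. An unadjusted iLet-arm difference then combines the effect of the mode with the difference in case mix. If TH happened to receive better-controlled people, a real TH disadvantage would be partly hidden and the groups would look similar. The opposite selection would create a disadvantage that is not there. Adding participants would not remove either error.

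For PC v EN the difficulty is structural: provider type, site and prior therapy change together, so no analysis of these data can separate them.

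The between-group estimates matter beyond this report, because section 2.2 says the glycemic data will be used to power a larger study.

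**Working it through.** **1. What each contrast contains**

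| Contrast | How the groups arise | What differs besides care model | Can a baseline covariate help? |
|---|---|---|---|
| TH v IP, within a practice | Preference, location, investigator discretion (2.1); video and internet access for TH only (3.1) | Unknown case mix | In part, for what is measured |
| PC v EN, within a mode | Site and therapy history (2.1, 3.1) | Site and population; possibly starting glucose target, since people coming from injections may start at the higher one (5.4.3) | No; neither site has both kinds of participant |
| iLet v usual care, within a group | Randomised order (5.5.3), paired tests (6.7) | Nothing by design | Not needed |

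The plan gives no power, margin or expected difference for the between-group comparisons (section 6.6), so it has no figure to reproduce beyond 2 practices × 2 modes × 10 = 40, which agrees.

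**2. How large a bias could be (illustration)**

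Inputs from the documents:
- 183 mg/dl corresponds to HbA1c 8.0% and 154 mg/dl to 7.0% (sections 6.2, 6.3).
- SD of mean CGM glucose is 13 mg/dl on the insulin-only iLet with lispro or aspart and 26 mg/dl in usual care (adult bridging study, Table 2).
- 10 participants per group.

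Assumptions, not in the documents:
- The groups differ by 0.5 to 1.0 percentage points of baseline HbA1c.
- A participant's iLet and usual-care mean glucose correlate at 0.3 to 0.6.

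Calculation:
- Glucose per point of HbA1c: 183 − 154 = 29 mg/dl.
- Baseline imbalance: 0.5 × 29 = 14.5 to 1.0 × 29 = 29 mg/dl.
- Share persisting on the iLet: correlation × 13/26, which is 0.15 to 0.30.
- Bias in the iLet-arm difference: 14.5 × 0.15 = 2.2 to 29 × 0.30 = 8.7 mg/dl.
- Standard error for 10 v 10: 13 × √(2/10) = 5.8 mg/dl; 95% half-width 12.2 mg/dl.

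The bias would be about 0.4 to 1.5 standard errors (2.2/5.8 to 8.7/5.8). It lies inside the 95% half-width throughout.

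**3. What that does to the reading**

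This uses a two-sample t-test with SD 13, 10 v 10 and an assumed two-sided 5% level. A true difference of 10 mg/dl gives p<0.05 in 37% of trials. If an imbalance offsets 5 mg/dl of it, that falls to 13%. With no true difference, a 5 mg/dl imbalance alone gives p<0.05 in 13%, instead of 5%. Finding no significant difference would therefore say little about similarity even without confounding, and confounding shifts the estimate itself.

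**The case against.** The plan is open about its limits. It calls itself a feasibility trial (section 6.6), says the groups are not randomised, offers p-values as an aid to reading and not for inference (section 6.7), and says the primary outcome does not directly compare mean glucose between groups (section 2.1). All of this stands and confines the point to secondary, descriptive comparisons. It does not answer it, because confounding distorts the estimate whatever use is made of the p-value.

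Section 6.7.2 says that all comparisons are between treatments within patients. Read literally, that would remove the between-group tests, but sections 2.2 and 6.7 plainly provide for them. The passages conflict, and the conflict needs resolving.

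Usual-care results by group will give a view of case mix, and baseline data will be summarised. That helps, but nothing commits the analysis to using either in the between-group comparisons.

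Three criticisms of HbA1c adjustment also stand. HbA1c does not measure preference, capability or internet access. Section 5.5.2 asks only for a validated method, not a common assay. Ordinary regression suits time below 54 mg/dl poorly, since that outcome is likely to be skewed: the bihormonal crossover study reported group means of only 0.3% and 0.6% (section 12.1.10).

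Section 12.1.8 reports that the iLet did equally well in injection and pump users. That argues against a large effect of therapy history but does not separate it from site and provider here.

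A reader might go further and infer that investigators will send better-controlled people to TH, that the plan claims to isolate the care model, or that the feasibility results are invalid. The documents support none of these. They give no direction of selection, they predict similarity without attributing it to the care model, and the within-group results do not rest on how the groups were formed.

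**Conclusion.** The concern holds for the between-group iLet-arm comparisons. They are unadjusted contrasts of non-randomised groups, although a relevant baseline value will be available for every participant. TH v IP can be improved in part. PC v EN cannot be repaired and compares care model together with population.

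The percentage below 183 mg/dl in each group remains a valid description of that group, and the randomised-order iLet v usual-care contrasts are untouched. The statement in section 6.7 that these percentages will not differ between groups carries the same limit on interpretation.

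Neither the size nor the direction of any bias is known. The range of about 2 to 9 mg/dl depends on the assumed imbalance and correlation, and its upper end needs both at their maximum. It shows only that the bias could be comparable with the 5.8 mg/dl standard error. The change is worth making because it is cheap; the point does not call the design into question.

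**What to change.** In section 6.7:
- For mean CGM glucose and time in 70–180 mg/dl, estimate the between-group iLet-arm differences by linear regression on all 40 participants, with terms for practice, visit mode, their interaction and baseline HbA1c. Report the four within-practice and within-mode differences with 95% confidence intervals beside the unadjusted ones.
- For time below 54 mg/dl, keep the rank test, or use a rank-based or transformed adjusted analysis.
- State that adjustment removes only measured case mix from TH v IP.
- State that PC v EN is descriptive and compares care model plus population. Carry the same sentence into sections 2.1 and 2.2.

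In section 6.7.2, reconcile the sentence on within-patient comparisons with the between-group tests in section 6.7.

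The cost is wording plus one extra model parameter: five coefficients including the intercept, leaving 40 − 5 = 35 residual degrees of freedom if all 40 contribute. The model assumes one HbA1c slope across the four groups, and the claim for PC v EN becomes more modest. Adjustment may also narrow the intervals, although a large imbalance would give some of that back. Design, sample size and visits do not change, and HbA1c is already collected.
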